10.5.2 Planned Interim Analysis

No interim analyses are planned for this study.

CONFIDENTIAL

STUDY DRUG(S): EVEROLIMUS
FINAL PROTOCOL DATE: 19 JUNE 2014

SCRI INNOVATIONS STUDY NUMBER: BRE 212
VERSION 1.0

10.5.3 Safety Review

No early safety reviews are planned for this study.

10.5.4 Efficacy Review

No early efficacy reviews are planned for this study.

10.6 Data Monitoring Committee

A Data Monitoring Committee (DMC) will not be utilized for this study.

10.7 Steering Committee

A Steering Committee will not be utilized for this study.

11. SAFETY REPORTING AND ANALYSES

Safety assessments will consist of monitoring and recording protocol-defined AEs and Serious Adverse Events (SAEs), measurement of protocol-specified hematology, clinical chemistry, and urinalysis variables, measurement of protocol-specified vital signs, and other protocol-specified tests that are deemed critical to the safety evaluation of the study drug.

The Principal Investigator is responsible for recognizing and reporting SAEs to the SCRI Innovations Safety Department (SD) (see Section 11.2). It is the Sponsor's responsibility to report relevant SAEs to the applicable local, national, or international regulatory bodies. In addition, Investigators must report SAEs and follow-up information to their responsible IRB/EC according to the policies of that IRB/EC.

The Principal Investigator is also responsible for ensuring that every staff member involved in the study is familiar with the content of this section.

11.1 Definitions

11.1.1 Adverse Events

Adverse event means any untoward medical occurrence associated with the use of a drug in humans, whether or not considered drug related. An adverse event (also known as adverse experience) can be any unfavorable and unintended sign (e.g., an abnormal laboratory finding), symptom, or disease temporarily associated with the use of a drug, without any judgement about causality. An adverse event can arise with any use of the drug (e.g., off-label use, use in combination with another drug) and with any route of administration, formulation, dose or including overdose.

CONFIDENTIAL

STUDY DRUG(S): EVEROLIMUS
FINAL PROTOCOL DATE: 19 JUNE 2014

SCRI INNOVATIONS STUDY NUMBER: BRE 212
VERSION 1.0

11.1.2 Serious Adverse Event

An AE or a suspected adverse reaction (SAR) is considered “serious” if it results in any of the following outcomes:

- **Death**
- **A life-threatening AE**
- **Inpatient hospitalization of at least 24-hours or prolongation of existing hospitalization**
- **A persistent or significant incapacity or substantial disruption of the ability to conduct normal life functions**
- **A congenital anomaly/birth defect**

Important medical events that may not result in death, be life-threatening, or require hospitalization may be considered serious when, based upon appropriate medical judgment, they may jeopardize the patient or subject and may require medical or surgical intervention to prevent one of the outcomes listed in this definition. Examples of such medical events include allergic bronchospasm requiring intensive treatment in an emergency room or at home, blood dyscrasias or convulsions that do not result in hospitalization, or development of drug dependency or drug abuse.

It is important to distinguish between “serious” and “severe” AE, as the terms are not synonymous. Severity is a measure of intensity; however, an AE of severe intensity need not necessarily be considered serious. Seriousness serves as the guide for defining regulatory reporting obligations. “Serious” is a regulatory definition and is based on patient/event outcome or action usually associated with events that pose a threat to a patient’s life or vital functions. For example, nausea which persists for several hours may be considered severe nausea, but may not be considered an SAE. On the other hand, a stroke which results in only a limited degree of disability may be considered only a mild stroke, but would be considered an SAE. Severity and seriousness should be independently assessed when recording AEs on the eCRF and SAEs on the SAE Report Form.

11.1.3 Adverse Reaction

An adverse reaction means any adverse event caused by a drug. Adverse reactions are a subset of all suspected adverse reactions where there is a reason to conclude that the drug caused the event.

11.1.4 Suspected Adverse Reaction

Suspected adverse reaction means any adverse event for which there is a reasonable possibility that the drug caused the adverse event. Reasonable possibility means that there is evidence to suggest a causal relationship between the drug and the adverse event. A suspected adverse reaction implies a lesser degree of certainty about causality than adverse reaction, which means any adverse event caused by a drug.

CONFIDENTIAL

STUDY DRUG(S): EVEROLIMUS
FINAL PROTOCOL DATE: 19 JUNE 2014

SCRI INNOVATIONS STUDY NUMBER: BRE 212
VERSION 1.0

11.1.5 Recording and Reporting of Adverse Events

Recording of Adverse Events

All AEs of any patient during the course of the research study will be recorded in the eCRF, and the investigator will give his or her opinion as to the relationship of the AE to the study drug treatment (i.e., whether the event is related or unrelated to study drug administration).

All AEs should be documented. A description of the event, including its date of onset and resolution, whether it constitutes a serious adverse event (SAE) or not, any action taken (e.g., changes to study treatment), and outcome, should be provided, along with the investigator's assessment of causality (i.e., the relationship to the study treatment[s]). For an AE to be a suspected treatment-related event there should be at least a reasonable possibility of a causal relationship between the protocol treatment and the AE. Adverse events will be graded according to the NCI CTCAE v4.0, and changes will be documented.

If the AE is serious, it should be reported immediately to SCRI Innovations SD. Other untoward events occurring in the framework of a clinical study are to be recorded as AEs (i.e., AEs that occur prior to assignment of study treatment that are related to a protocol-mandated intervention, including invasive procedures such as biopsies, medication washout, or no treatment run-in).

Any clinically significant signs and symptoms; abnormal test findings; changes in physical examination; hypersensitivity; and other measurements that occur will be reported as an AE, and collected on the relevant eCRF screen.

Test findings will be reported as an AE if: the test result requires an adjustment in the study drug(s) or discontinuation of treatment, and/ or test findings require additional testing or surgical intervention, a test result or finding is associated with accompanying symptoms, or a test result is considered to be an AE by the investigator.

Reporting Period for Adverse Events

All AEs regardless of seriousness or relationship to everolimus treatment (called study treatment), spanning from the start of study treatment, until 30 calendar days after discontinuation or completion of study treatment as defined by the clinical study for that patient, are to be recorded on the corresponding screen(s) included in the eCRF.

All AEs resulting in discontinuation from the study should be followed until resolution or stabilization. All new AEs occurring during this period must be reported and followed until resolution unless, in the opinion of the investigator, the AE or laboratory abnormality/ies are not likely to improve because of the underlying disease. In this case, the investigators must record his or her reasoning for this decision in the patient's medical record and as a comment on the eCRF screen.

After 30 days of completion of protocol-specific treatment or discontinuation, only AEs, SAEs, or deaths assessed by the investigator as treatment related are to be reported.

11.1.6 Assessment of Adverse Events

All AEs and SAEs whether volunteered by the patient, discovered by study personnel during questioning, or detected through physical examination, laboratory test, or other means will be

CONFIDENTIAL

STUDY DRUG(S): EVEROLIMUS
FINAL PROTOCOL DATE: 19 JUNE 2014

SCRI INNOVATIONS STUDY NUMBER: BRE 212
VERSION 1.0

reported appropriately. Each reported AE or SAE will be described by its duration (i.e., start and end dates), regulatory seriousness criteria if applicable, suspected relationship to the study drug (see following guidance), and actions taken.

To ensure consistency of AE and SAE causality assessments, investigators should apply the following general guideline:

YES: There is a plausible temporal relationship between the onset of the AE and administration of the study medication, and the AE cannot be readily explained by the patient's clinical state, intercurrent illness, or concomitant therapies, and/or the AE follows a known pattern of response to the study drug, and/or the AE abates or resolves upon discontinuation of the study drug or dose reduction and, if applicable, reappears upon re-challenge.

NO: Evidence exists that the AE has an etiology other than the study drug (e.g., pre-existing medical condition, underlying disease, intercurrent illness, or concomitant medication), and/or the AE has no plausible temporal relationship to study drug administration (e.g., cancer diagnosed 2 days after first dose of study drug).

11.2 Serious Adverse Event Reporting by Investigators

Adverse events classified by the treating investigator as serious require expeditious handling and reporting to SCRI Innovations Safety Department in order to comply with regulatory requirements. Determination of life-threatening or serious is based on the opinion of either the Sponsor or the Investigator.

Serious AEs may occur at any time from the start of study treatment through the 30 day follow-up period after the last study treatment. **The SCRI Innovations Safety Department must be notified of all SAEs, regardless of causality, within 24 hours of the first knowledge of the event by the treating physician or research personnel.**

To report a SAE, the SAE Report Form should be completed with the necessary information.

The SAE report should be sent to SCRI Innovations Safety Department via fax or e-mail using the following contact information (during both business and non-business hours):

SCRI Innovations Safety Department
Safety Dept. [contact]
Safety Dept. Email: [contact]

Transmission of the SAE report should be confirmed by the site personnel submitting the report.

Follow-up information for SAEs and information on non-serious AEs that become serious should also be reported to SCRI Innovations Safety Department as soon as it is available; these reports should be submitted using the SCRI Innovations SAE Report Form. The detailed SAE reporting process will be provided to the sites in the SAE reporting guidelines contained in the study reference manual.

Investigators must report SAEs and follow-up information to their responsible IRB according to the policies of the responsible IRB.

CONFIDENTIAL

STUDY DRUG(S): EVEROLIMUS
FINAL PROTOCOL DATE: 19 JUNE 2014

SCRI INNOVATIONS STUDY NUMBER: BRE 212
VERSION 1.0

11.3 Recording of Adverse Events and Serious Adverse Events

11.3.1 Diagnosis versus Signs and Symptoms

All AEs should be recorded individually in the patient's own words (verbatim) unless, in the opinion of the Principal Investigator or designated physician, the AEs constitute components of a recognized condition, disease, or syndrome. In the latter case, the condition, disease, or syndrome should be named rather than each individual sign or symptom. If a constellation of signs and/or symptoms cannot be medically characterized as a single diagnosis or syndrome at the time of reporting, each individual event should be recorded as an AE or SAE as appropriate on the relevant form(s) (SAE Report Form and/or AE eCRF screen). If a diagnosis is subsequently established, it should be reported as follow-up information is available. If a diagnosis is determined subsequent to the reporting of the constellation of symptoms, the signs/symptoms should be updated to reflect the diagnosis.

Progression of malignancy (including fatal outcomes), if documented by use of appropriate method (for example, as per RECIST criteria for solid tumors), should not be reported as an SAE.

11.3.2 Persistent or Recurrent Adverse Events

A persistent AE is one that extends continuously, without resolution, between patient evaluation time points. Such events should only be recorded once on the SAE Report Form and/or the AE eCRF screen. If a persistent AE becomes more severe or lessens in severity, it should be recorded on a separate SAE Report Form and/or AE eCRF screen.

A recurrent AE is one that occurs and resolves between patient evaluation time points, and subsequently recurs. All recurrent AEs should be recorded on an SAE Report Form and/or AE eCRF screen.

11.3.3 Abnormal Laboratory Values

If an abnormal laboratory value or vital sign is associated with clinical signs and/or symptoms, the sign or symptom should be reported as an AE or SAE, and the associated laboratory value or vital sign should be considered additional information that must be collected on the relevant eCRF screen. If the laboratory abnormality is a sign of a disease or syndrome, only the diagnosis needs to be recorded on the SAE Report Form or AE eCRF screen.

Abnormal laboratory values will be reported as an AE if: the laboratory result requires an adjustment in the study drug(s) or discontinuation of treatment, and/ or laboratory findings require additional testing or surgical intervention, a laboratory result or finding is associated with accompanying symptoms, or a laboratory result is considered to be an AE by the investigator.

11.3.4 Deaths

Deaths that occur during the protocol-specified AE reporting period that are attributed by the Investigator solely to progression of disease will be recorded on the "Study Discontinuation" eCRF screen. All other on study deaths, regardless of attribution, will be recorded on an SAE Report Form and expeditiously reported to the SCRI Innovations Safety Department.

CONFIDENTIAL

STUDY DRUG(S): EVEROLIMUS
FINAL PROTOCOL DATE: 19 JUNE 2014

SCRI INNOVATIONS STUDY NUMBER: BRE 212
VERSION 1.0

When recording a SAE with an outcome of death, the event or condition that caused or contributed to the fatal outcome should be recorded as the single medical concept on the SAE Report Form and Adverse Event screen of the eCRF. If the cause of death is unknown and cannot be ascertained at the time of reporting, record “Death NOS” on the eCRF Adverse Event screen. During post-study survival follow-up, deaths attributed to progression of disease will be recorded only on the “After Progressive Disease Follow-Up” eCRF screen.

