6.2.9 Management of Non-Infectious Pneumonitis

Non-infectious pneumonitis is a class effect of rapamycin derivatives. Cases of non-infectious pneumonitis (including interstitial lung disease) have also been described in patients taking

CONFIDENTIAL

STUDY DRUG(S): EVEROLIMUS
FINAL PROTOCOL DATE: 19 JUNE 2014

SCRI INNOVATIONS STUDY NUMBER: BRE 212
VERSION 1.0

everolimus. Some of these have been severe and on rare occasions, a fatal outcome was observed.

- A diagnosis of non-infectious pneumonitis should be considered in patients presenting with non-specific respiratory signs and symptoms such as hypoxia, pleural effusion, cough or dyspnea, and in whom infectious, neoplastic and other non-medicinal causes have been excluded by means of appropriate investigations. Opportunistic infections such as PJP should be ruled out in the differential diagnosis of non-infectious pneumonitis. Patients should be advised to report promptly any new or worsening respiratory symptoms.

Patients who develop radiological changes suggestive of non-infectious pneumonitis and have few or no symptoms may continue everolimus therapy without dose alteration.

If symptoms are moderate (grade 2), consideration should be given to interruption of therapy until symptoms improve. The use of corticosteroids may be indicated. Everolimus may be reintroduced at a daily dose approximately 50% lower than the dose previously administered.

For cases of grade 3 non-infectious pneumonitis, interrupt everolimus until resolution to less than or equal to grade 1. Everolimus may be re-initiated at a daily dose approximately 50% lower than the dose previously administered depending on the individual clinical circumstances. If toxicity recurs at grade 3, consider discontinuation of everolimus. For cases of grade 4 non-infectious pneumonitis, everolimus therapy should be discontinued. Corticosteroids may be indicated until clinical symptoms resolve.

For patients who require use of corticosteroids for treatment of non-infectious pneumonitis, prophylaxis for pneumocystis jirovecii pneumonia (PJP) may be considered. The two compounds studied most extensively for prophylaxis against PJP have been trimethoprim-sulfamethoxazole, given orally, and pentamidine, given as an aerosol.

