11.3.7 New Cancers

The development of a new primary cancer should be regarded as an AE and will generally meet at least one of the seriousness criteria (see Section 11.2). New primary cancers are those that are not the primary reason for the administration of the study treatment and have developed after the inclusion of the patient into the study. They do not include metastases of the original cancer. Symptoms of metastasis or the metastasis itself should not be reported as an AE/SAE, as they are considered to be disease progression.

CONFIDENTIAL

STUDY DRUG(S): EVEROLIMUS
FINAL PROTOCOL DATE: 19 JUNE 2014

SCRI INNOVATIONS STUDY NUMBER: BRE 212
VERSION 1.0

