Table 5	Treatment and Dose Modifications	Duration on Treatment (weeks), N, Mean, SD, Median, Min, Max Dose Reduction (n, %) None Patients with 1 Patients with 2 Patients with >= 3 Dose Interruption (n, %) None Patients with 1 Patients with 2 Patients with >= 3	Safety
Table 6	Measurable Lesions	Measurable Lesions (n, %) Non-Measurable Lesions (n, %) Evaluable Bone Only Disease (n, %)	Enrolled Patients
Table 7	Best Overall Response	Best overall response (n, %): Complete response (CR), Partial response (PR), Stable disease (SD), NonCR/NonPD, Progressive disease (PD), Not evaluable (NE), Not applicable (N/A) Missing Objective Response Rate (ORR) (= CR+PR): ORR, 95% Confidence interval Clopper-Pearson	Efficacy Evaluable, Safety

Standard TFLs			
Table No	Description	Variables/Analyses To Be Included	Population
		Normal Approximation Clinical Benefit Rate (CBR) $(=CR+PR+SD \geq 4 \text{ months})$: CBR, 95% Confidence interval Clopper-Pearson Normal Approximation Clinical Benefit Rate (CBR) $(=CR+PR+SD \geq 6 \text{ months})$: CBR, 95% Confidence interval Clopper-Pearson Normal Approximation]	
Table 8	Progression-free Survival (Kaplan-Meier estimates & 95% CI)	Number of patients with events, Number of patients censored, Median Progression-free Survival [months (95% CI)] 25% Percentile Follow-up [months (95% CI)] 75% Percentile Follow-up [months (95% CI)] Progression-free Survival Estimates [probability, (95% CI)]: 4 months, 6 months, 12 months	Efficacy Evaluable, Safety
Table 9	Overall Survival (Kaplan-Meier estimates & 95% CI)	Number of patients with events, Number of patients censored, Median Overall Survival [months (95% CI)] 25% Percentile Follow-up [months (95% CI)] 75% Percentile Follow-up [months (95% CI)] Overall Survival Estimates [probability, (95% CI)]: 4 months, 6 months, 12 months	Efficacy Evaluable, Safety
Table 10	Adverse Event Overview	Any Adverse Event Treatment-related Adverse Event Everolimus-related Adverse Event Anti-Estrogen Therapy-related Adverse Event Serious Adverse Event Treatment-related Serious Adverse Event Serious Adverse Event leading to Death Treatment-related Serious Adverse Event leading to Death Adverse Events leading to Treatment Discontinuation Adverse Events leading to Treatment Interruption Adverse Events leading to Treatment Reduced	Safety

Standard TFLs			
Table No	Description	Variables/Analyses To Be Included	Population

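### Sections 11.3.1 and 11.3.4 set different conditions for keeping a death off the SAE form, so a death attributed to progression without documentation is missing from the fatal-SAE rows of SAP Table 10

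*Protocol*

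**What the plan says.** Two sections of the protocol govern whether a death from disease is reported as an SAE.

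- Section 11.3.1 says that progression of malignancy, fatal outcomes included, "if documented by use of appropriate method (for example, as per RECIST criteria for solid tumors), should not be reported as an SAE". The exemption depends on documentation.
- Section 11.3.4 says: "Deaths that occur during the protocol-specified AE reporting period that are attributed by the Investigator solely to progression of disease will be recorded". Their place is the Study Discontinuation eCRF screen. The next sentence of that section begins: "All other on study deaths, regardless of attribution, will be recorded on an SAE Report Form". Here the exemption depends on the investigator's attribution alone, and there is no reference back to 11.3.1.

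The general rules are in 11.1.2, where death is a seriousness criterion, and 11.2, where every SAE must be notified to the sponsor's safety department within 24 hours whatever its cause. Section 11.1.5 sets the AE reporting period from the start of study treatment to 30 days after it ends.

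On the analysis side, SAP Table 10 (Adverse Event Overview) has a row for "Serious Adverse Event leading to Death" and a second row for the treatment-related subset. Neither the SAP's 18 tables nor its four listings show all deaths by cause within 30 days of the last dose.

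**The concern.** Whether a death becomes an SAE should not depend on which of two sections the site consults. A site with a death to record will naturally turn to the section headed Deaths, and that one has the looser condition.

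The case can arise. Scheduled imaging is every 8 weeks and starts before Cycle 3, so a patient who dies before the first restaging has no scheduled post-baseline scan to support an attribution to progression. The protocol also acknowledges fatal pneumonitis (6.2.9), infection (6.2.1) and renal failure (6.2.5) on everolimus, so the attribution matters.

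What is at stake is the safety record. Without an SAE form there is no 24-hour notice, and the forwarding of SAE information to the drug supplier (11.5) and the expedited-reporting assessment (11.5.1) are not set in motion by the site. Safety and tolerability is the secondary objective. There is no control arm and no DMC, so the two fatal rows of Table 10 carry much of the information about fatal toxicity.

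**Working it through.** There is no figure in the plan to reproduce. The check is a comparison of the rules, followed by a calculation of scale.

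**Step 1: the rules side by side, for a death in the AE reporting period.**

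| Death | 11.3.1 | 11.3.4 | Agree? |
|---|---|---|---|
| Attributed solely to progression, progression documented | Exempt | Exempt | Yes |
| Attributed solely to progression, progression not documented | Exemption does not apply | Exempt | No |
| Attributed to anything else, or only partly to progression | Exemption does not apply on its face | SAE form | Yes |
| Cause unknown | Not addressed | Death NOS on the AE screen; SAE form as one of the other deaths | No conflict |

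In the second row 11.3.1 is silent rather than contrary. The duty to report comes from 11.1.2 and 11.2 once the exemption falls away.

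**Step 2: where a second-row death is recorded under 11.3.4.**

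- Study Discontinuation eCRF screen: yes, and so potentially under reason for study discontinuation in SAP Table 1.
- Overall survival: yes, as an event in any analysis population that includes the patient (SAP Table 9 is planned for the Efficacy Evaluable and Safety populations).
- PFS: an event if there was no earlier progression and no subsequent therapy.
- SAE form and 24-hour notice: no.
- Both fatal rows of SAP Table 10: no, because they count SAEs.

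**Step 3: scale.** Inputs: n = 46, the planned enrolment (protocol 10.2), assuming that all are treated; x = number of fatal SAEs shown, taken as 0 to 2 because the documents give no number. Exact (Clopper-Pearson) two-sided 95% limits are: lower = Beta quantile 0.025 with parameters (x, n − x + 1), or 0 when x = 0; upper = Beta quantile 0.975 with parameters (x + 1, n − x). For x = 0 the upper limit reduces to 1 − 0.025^(1/46) = 7.7%.

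| x | x/46 | Exact 95% interval |
|---|---|---|
| 0 | 0% | 0% to 7.7% |
| 1 | 2.2% | 0.06% to 11.5% |
| 2 | 4.3% | 0.5% to 14.8% |

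One death moved off the SAE form takes the display from the second line to the first. Table 10 specifies no confidence limits, so these intervals only indicate how much one event weighs in a study of this size.

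**The case against.** The best defence is that the sections can be read together, with 11.3.1 setting the evidence standard and 11.3.4 only naming the screen. That does not quite work. Section 11.3.4 also decides which deaths go on the SAE form, by sending only the other deaths there, and it does so without the documentation condition. The difference remains, although it is fair to say that the sections are misaligned rather than giving opposite commands.

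Several further points on that side stand and limit the concern.

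- The word solely narrows the exemption. Mixed attributions go to the SAE form, and an unknown cause is entered as Death NOS.
- A reader might infer that a fatal toxicity would go unreported altogether. The documents do not support that. The death is on the eCRF, which is to be kept current for sponsor review (14.4), and under 11.2 the sponsor as well as the investigator may judge an event serious. A toxicity recognised before death is reportable in its own right.
- Section 6.2.9 lists "non-specific respiratory signs and symptoms such as hypoxia, pleural effusion, cough or dyspnea" as presenting features of pneumonitis, which suggests confusion with tumour. The same sentence, however, requires infectious, neoplastic and other causes to have been excluded by investigation, and Table 5 specifies CT at every grade.
- The 8-week argument concerns scheduled scans. The SAP allows for progression documented between visits, and the end-of-treatment visit includes CT.
- A reader might also want 11.3.7 changed, since it says: "Symptoms of metastasis or the metastasis itself should not be reported as an AE/SAE, as they are considered to be disease progression". That sentence separates new primaries from metastases of the original cancer, and 11.1.6 guides causality for events already reported as AEs. Whether disease symptoms should also be collected as unrelated AEs is a preference on which reasonable reviewers differ.

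**Conclusion.** The point holds in a limited form. The protocol has two conditions for the same exemption, and they part for a death attributed solely to progression without documented progression. Such a death remains in the database and can count for overall survival, but it is outside SAE reporting and outside both fatal rows of Table 10.

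The size is unknown. Each such death is 2.2 percentage points if all 46 planned patients are treated; the range of 0 to 2 deaths is an assumption. A reader might go further and infer that the fatal-toxicity result will be biased towards a safer-looking combination. The documents give no rate of misattribution, so they show a possible undercount, not a bias. The efficacy endpoints gain or lose no event through this gap, since the death is recorded either way.

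The matter should be corrected: the conflict is plain in the text and the repair is cheap. It is a reporting gap and does not undermine the design.

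**What to change.** 1. In protocol 11.3.4, carry over the condition in 11.3.1. A death in the AE reporting period is exempt from the SAE form only if the investigator attributes it solely to progression and the progression is documented by an appropriate method (for example RECIST). Every other death in that period goes on an SAE form with the investigator's causality. A cross-reference between the two sections would keep them aligned.
2. In the SAP, add to Table 10 a row, or provide a listing, of all deaths from first dose to 30 days after last study treatment, with attributed cause and documented progression yes/no.

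No change to 11.3.7 is needed for this point.

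The cost is a wording amendment, one extra row or listing, and a few additional SAE forms. Some true disease deaths without documentation will enter the fatal-SAE row and make it less specific for toxicity; the yes/no split makes them visible. One limit remains: documented progression does not itself establish the cause of death, so a patient with progression who dies of a toxicity taken for disease would still be exempt. Listing all deaths at least allows such cases to be re-examined.
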